7.4 Rules and Definition

7.4.1 General

For baseline categorical variables, “unknown” responses and missing values will not be counted in rate denominators

7.4.2 Body Mass Index (BMI)

In case the weight is calculated in “lbs” and/or height in “in” then the following formula will be used to convert into kg and cm, respectively.

$$\text{Weight (Kg)} = \text{Weight (lbs)} / 2.20462262.$$

$$\text{Height (cm)} = \text{Height (in)} / 0.393700787$$

$$BMI = \frac{\text{Weight (Kg)} \times 10000}{(\text{Height (cm)})^2}$$

7.4.3 Denominator using Sufficient Follow-up for Endpoints and Additional Measurements

All subjects in the specific analysis sets (ITT or PP) will be included in the denominator for the analysis for the primary endpoint and additional measurements. All subjects are considered as having sufficient follow-up through 72 hours or hospital discharge, whichever comes first.

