5.1.3. Vortex Console

[REDACTED]

[REDACTED]

5.2. *Device Labeling*

A copy of the Vortex IFU is included in the study Manual of Operations.

Packaging includes peelable, self-adhesive labels applied to both the sterile barrier pouch and the carton for each unit shipped. The labels on the shelf cartons and sterile pouch include the following information.

- Product name
- Product number
- Lot number or serial number
- Expiration date (use by) date (labeled as month/year, device not to be used after the last day of the indicated month)

The following statement appears on the study device product labeling:

Exclusively for Clinical Investigations.

5.3. *Ancillary Devices and Procedures*

The Vortex System requires the use of several medical instruments to ensure correct delivery and positioning of the pump and other devices to characterize pump performance during use. Please see the Investigator's Brochure for a list of devices that may be used with the Vortex System.

6. Study Objectives and Endpoints

6.1. *Objectives*

The objective of the Vortex feasibility study is to evaluate the feasibility and safety of the Vortex Temporary Percutaneous Transvalvular Circulatory Support System (Vortex System) in subjects undergoing elective HR-PCI.

6.2. *Primary Endpoint*

The primary endpoint consists of Technical Success and Clinical Success, defined as follows.

Technical Success

- Successful delivery of the device to the correct anatomical position; and
- Successful operation and removal of the Vortex circulatory support system

Clinical Success

- No conversion to open heart surgery; and

- No in-hospital mortality (see *Note 1* in Section 6.3)

6.3. *Additional Measurements*

Safety events will be collected through 72 hours post-procedure or hospital discharge, whichever comes first, as listed below.

- Stroke/transient ischemic attack (TIA; see *Note 1* below)
- Cardiac tamponade
- Cardiac death (see *Note 1* below)
- Myocardial infarction (MI)
- Bleeding complications: Type 3–5 based on the Mechanical Circulatory Support Academic Research Consortium (MCS-ARC)²⁸ definitions (see *Note 1* below)
- Acute kidney injury (AKI; based on the AKIN^{29,30} System Stage 3 [including renal replacement therapy] or Stage 2)
- Major vascular complications (see *Note 1* below)
- Any device-related adverse event (adverse device effect [ADE]/serious adverse device effect [SADE])
- Any procedure-related adverse event
- Any adverse event related to management practices

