7.2. Treatment Assignment

7.3. Subjects who are candidates for high-risk percutaneous coronary intervention, provide written informed consent, and are eligible to be treated with the Vortex System will be evaluated for enrollment in this study. Prior to being eligible for

the study, a subject must meet all of the inclusion criteria (Section 8.2) and none of the exclusion criteria (Section 8.3). Justification for the Study Design

In order to provide an assessment of safety and performance of the Vortex System while also limiting the potential exposure of study subjects to risk, the sample size in this feasibility study has been limited to up to 10 subjects at up to 3 investigative centers in Australia and Europe. Technical Success, Clinical Success, and safety results will be reported on all enrolled subjects through 72 hours or hospital discharge, whichever comes first.

8. Subject Selection

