d: 12-lead ECG; baseline ECG should be done within 30 days prior to the index procedure; post-procedure timing is per standard of care for HR-PCI.

e: Laboratory tests at baseline include CBC with platelets, serum creatinine, plasma-free hemoglobin, and cardiac enzymes. Post-procedure, cardiac enzymes (CK or troponin is required, CK-MB or troponin if CK is elevated) must be collected once per standard of care within 6–24 hours; if readings are abnormal, a second collection per standard of care is required. Plasma-free hemoglobin must be collected pre-discharge (≥ 6 hours post procedure). Plasma-free hemoglobin may be collected during the index procedure per the standard of care.

f: Minimum required iliofemoral diameter is > 5.5 mm; any assessment technique to determine diameter and tortuosity is permitted; assessment must be done within 365 days prior to the index procedure.

g: TTE assessment should be done within 180 days prior to the index procedure.

h: Deidentified copies of the imaging assessments should be provided to Boston Scientific.

i: Coronary angiogram should be done within 365 days prior to the index procedure per standard of care for HR-PCI.

j: Information on device deficiencies for the test device will be monitored and reported to Boston Scientific.

k: The adverse event assessment includes AE, SAE, ADE, SADE, USADE, and IMR events, which will be collected from the time of enrollment through 72 hours post-procedure or hospital discharge, whichever comes first, in all subjects. Please refer to Section 18.1 for reportable events, including a list of IMR events, and to **Table 24.2-1** for definitions of these events, which specify data required for IMR adjudication.

Abbreviations: AE=adverse event; ADE=adverse device effect; CBC=complete blood count; CCS=Canadian Cardiovascular Society; CK=creatinine kinase; CK-MB=creatinine kinase myoglobin band; ECG=electrocardiogram; HR-PCI=high risk percutaneous coronary intervention; IMR=independent medical

Table 10.1-1: Data Collection Schedule

Assessment	Baseline	Index Procedure	≤72 Hours / Discharge ^a
------------	----------	-----------------	------------------------------------

reviewer; SADE=serious adverse device effect; SAE=serious adverse event; USADE=unanticipated serious adverse device effect

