10.7.3. Intraprocedural Hemodynamic Measurements

Intraprocedural hemodynamic assessment is primarily based on TTE (or intracardiac echocardiography³³ as per standard of care) and catheter-based pulmonary artery measurements. Cardiac output (CO), pulmonary artery (PA) pressure, pulmonary capillary wedge pressure (PCWP), central venous pressure (CVP), mean arterial pressure (MAP), and right atrial pressure (RAP) should be measured before and after the pump is placed and switched on via the pulmonary artery catheter and also when the pump is switched off and

removed (post-procedure). Left ventricular pressure may be measured via the pigtail catheter.

10.8. *Post-procedure (≤ 72 Hours)/Prior to Hospital Discharge*

Within 72 hours post procedure or before discharge (whichever comes first), the following assessments must be performed.

- 12-lead ECG
- Laboratory tests
 - Cardiac enzymes (CK or troponin required, CK-MB or troponin if CK is elevated) must be collected once per standard of care within 6–24 hours post-procedure; if readings are abnormal, a second collection per standard of care is required.
 - Plasma-free hemoglobin must be collected ≥ 6 hours post procedure (before discharge)
- NYHA classification
- Anticoagulation therapy and other cardiovascular medications
- Adverse event assessment (see Section 18)
- Device deficiencies assessment

10.9. *Study Completion*

All subjects will be evaluated through 72 hours or hospital discharge, whichever comes first. A subject's participation in the study will be considered complete after 72 hours or hospital discharge (whichever comes first).

10.10. *Source Documents*

It is preferable that original source documents, when available, are maintained at the investigative center. In lieu of original source documents, certified copies are required to be maintained. A certified copy is a copy (irrespective of the type of media used) of the original record that has been verified (i.e., by a dated signature or by generation through a validated process) to have the same information, including data that describe the context, content, and structure, as the original. Source documentation includes but is not limited to those items noted in **Table 10.10-1**. Source documentation provided to the Sponsor for assessment/adjudication will be deidentified per local law and regulations.

Table 10.10-1: Source Documentation Requirements

Requirement	Disposition

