11.1. Endpoints

11.1.1. Primary Endpoint

The primary endpoint consists of Technical Success and Clinical Success. Technical Success is defined as successful delivery of the device to the correct anatomical position and successful operation and removal of the Vortex System. Clinical Success is defined as no conversion to open heart surgery or in-hospital mortality.

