24.2. Definitions

Terms are defined in **Table 24.2-1**.

Table 24.2-1: Definitions

Term	Definition
ACUTE KIDNEY INJURY (AKI) (AKIN System ^{29,30})	
Maximal change in serum creatinine from baseline through discharge or 72 hours post-procedure, whichever comes first.
 
 • Stage 1: Increase in serum creatinine to 150–199% (1.5–1.99 × increase compared with baseline) OR increase of ≥0.3 mg/dl (≥26.4 mmol/L), or urine output <0.5 ml/kg per hour for >6 but <12 hours • Stage 2: Increase in serum creatinine to 200–299% (2.0–2.99 × increase compared with baseline) or urine output <0.5 ml/kg per hour for >12 but <24 hours • Stage 3: Increase in serum creatinine to ≥300% (>3 × increase compared with baseline) OR serum creatinine of ≥4.0 mg/dL (≥354 mmol/L) with an acute increase of at least 0.5 mg/dL (44 mmol/L) OR urine output <0.3 ml/kg per hour for ≥24 hours or anuria for ≥12 hours 
Note: Subjects receiving renal replacement therapy are considered to meet Stage 3 criteria irrespective of other criteria.

ACUTE VESSEL OCCLUSION	The state of complete luminal obstruction with no antegrade blood flow.
ADVERSE EVENT (AE) Ref: ISO 14155	Any untoward medical occurrence, unintended disease or injury, or any untoward clinical signs (including an abnormal laboratory finding) in subjects, users or other

Table 24.2-1: Definitions

[figure not shown]
Term	Definition

Ref: MDCG 2020-10/1
	
persons, in the context of a clinical investigation, whether or not related to the investigational medical device and whether anticipated or unanticipated.
 
Note 1: This includes events related to the investigational medical device or the comparator.
 
Note 2: This definition includes events related to the procedures involved.
 
Note 3: For users or other persons, this definition is restricted to events related to the investigational medical device.
 
Note 4: This definition includes events related to management practices.
 
Note 5: This definition includes patient related events.

ADVERSE EVENT BECOME AWARE DATE
	
The become aware date for an adverse event that requires reporting per the protocol is the date that study personnel listed on the Delegation of Authority Log identify or are notified of the event.

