
Table 24.2-1: Definitions

Term	Definition
	
 • Health plan beneficiary numbers • Full-face photographs and any comparable images • Any other unique identifying number, characteristic, or code (including subject ID number)
DEATH	
All-cause Death Death from any cause after percutaneous coronary intervention using circulatory support. Death is categorized as cardiac or non-cardiac.
 
Cardiac Death Cardiac death is defined as death due to any of the following.
 
 • Acute myocardial infarction • Cardiac perforation/pericardial tamponade • Arrhythmia or conduction abnormality • Cerebrovascular accident (CVA) through hospital discharge or CVA suspected of being related to the procedure • Death due to complication of the procedure, including bleeding, vascular repair, transfusion reaction, or bypass surgery • Any death in which a cardiac cause cannot be excluded 
Non-cardiovascular Death Non-cardiac death is defined as a death not due to cardiac causes as defined above.

DEVICE DEFICIENCY Ref: ISO 14155 Ref: MDCG 2020-10/1	
An inadequacy of an investigational medical device related to its identity, quality, durability, reliability, safety or performance.
 
Note 1: Device deficiencies include malfunctions, use errors, or inadequacy in the information supplied by the manufacturer.

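### Clinical Success counts in-hospital deaths with no time limit, but event collection, results and follow-up stop at 72 h, so a later in-hospital death may be left out

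*SAP*

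**What the plan says.** **The endpoint.** Protocol 6.2, the Clinical Success entry in Protocol Table 24.2-1 and SAP 3.1 list the mortality component as "No in-hospital mortality". Protocol 11.1.1 says: "Clinical Success is defined as no conversion to open heart surgery or in-hospital mortality". None of these gives a time limit.

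**The window.** Four other places end at the earlier of 72 h and discharge:

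- Protocol Table 10.1-1, note k, on adverse events and events sent to the Independent Medical Reviewer: "which will be collected from the time of enrollment through 72 hours post-procedure or hospital discharge, whichever comes first, in all subjects".
- Protocol 10.9, on each subject: "participation in the study will be considered complete after 72 hours or hospital discharge (whichever comes first").
- Protocol 7.3, which names the endpoint: "Technical Success, Clinical Success, and safety results will be reported on all enrolled subjects through 72 hours or hospital discharge, whichever comes first".
- SAP 7.4.3, which puts all ITT or per-protocol subjects in the primary-endpoint denominator and then states: "All subjects are considered as having sufficient follow-up through 72 hours or hospital discharge, whichever comes first".

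**Investigator reporting.** Protocol 18.1 and Table 18.4-1 run reporting from enrollment to the end of the study. Protocol 9.3 defines that end for the study as a whole, not for each subject.

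**The concern.** The label promises survival to discharge, while the operational text delivers survival to 72 h for anyone who stays longer. An analyst following Protocol 7.3 and SAP 7.4.3 could report 72 h survival under an in-hospital heading.

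The error runs one way: leaving out a late death can only raise Clinical Success. The subjects exposed are those with stays beyond 72 h, which may include the ones who did poorly. This is a first-human-use study intended to assess device safety, so the survival component should mean what it says.

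The other component, conversion to open heart surgery, also has no window in its definition. A restriction to the HR-PCI procedure appears only in the rationale column of Protocol Table 6.4-1.

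**Working it through.** The plan has no derived figure to reproduce. The maximum of 10 subjects is described as arbitrary, and there is no hypothesis, alpha or power. The check is therefore a comparison of texts, followed by arithmetic for scale.

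**1. Is the missing limit just house style?** No. Where the authors wanted the cap, they wrote it in. Protocol Table 24.2-1 defines acute kidney injury as "Maximal change in serum creatinine from baseline through discharge or 72 hours post-procedure, whichever comes first", and the Type 4 bleeding criteria carry the same cap. The all-cause death entry has none. One cardiac-death criterion reads "Cerebrovascular accident (CVA) through hospital discharge". That criterion classifies cause of death and does not set follow-up, so it is weak support, but it shows the table uses discharge as a separate time point.

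**2. What happens to each kind of subject?**

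| Subject | By the endpoint's label | By Protocol 7.3, 10.9 and note k |
|---|---|---|
| Leaves hospital before 72 h | Observed to discharge | Same; the windows coincide |
| In hospital at 72 h, later discharged alive | Success | Success |
| In hospital at 72 h, dies there on day 5 (hypothetical) | Failure | Outside the window, but still in the SAP 7.4.3 denominator |

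The conflict is confined to the last row. No section requires vital status at discharge for that subject.

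**3. Effect of one uncounted death.** All other subjects are assumed to succeed.

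- n = 10: 9/10 = 0.900 becomes 10/10 = 1.000. For reference, the exact 95% intervals are 55.5% to 99.7% and 69.2% to 100%; the SAP does not call for intervals.
- n = 5 (assumed, because enrollment is capped at 10 but may be lower): 4/5 = 0.800 becomes 5/5 = 1.000.

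**4. How likely is a late death?** The documents do not say. As an illustration only, let p be the in-hospital mortality of the two registries in Protocol 4.1.2 that report it (2.6% and 3.4%, both for another device). Let f be the unknown share of those deaths that fall after 72 h. For 10 subjects:

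P(at least one late in-hospital death) = 1 − (1 − p·f)^10

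| p | f = 0 | f = 0.5 | f = 1 |
|---|---|---|---|
| 0.026 | 0 | 1 − 0.987^10 = 0.123 | 1 − 0.974^10 = 0.232 |
| 0.034 | 0 | 1 − 0.983^10 = 0.158 | 1 − 0.966^10 = 0.292 |

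The f = 1 column is also the chance of any in-hospital death. The late-death probability lies between 0 and that figure, and another mortality rate would move the range.

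**The case against.** The strongest reply is that Protocol 7.3 already sets a window for Clinical Success by name, and note k, 10.9 and SAP 7.4.3 agree with it. On that reading the fault is a label that is too broad. This is a fair reading, but the label would then have to change, because a reader of the results would take in-hospital mortality literally.

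Second, many late deaths would reach the sponsor. Protocol 18.1 covers events to the end of the study, asks for updates to events already reported and records death as the outcome of a serious adverse event. Closeout monitoring checks ongoing events. Much of this stands. A death from an event that began before 72 h should surface, and on the wording of 18.1 so should many that began later. But 18.1 disagrees with note k and 10.9 on when a subject's reporting ends. A study-level end is not tied to each subject's discharge and gives the last subject no extra cover. The clearer gap is a death from an event that starts after 72 h.

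Third, SAP 7.4.3 is a denominator rule, and SAP 7.3 includes all data not judged invalid. That favours counting a recorded late death, while Protocol 7.3 points the other way. The SAP does not settle which governs.

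Fourth, the eCRF and the reviewer's charter are not among the documents, so a discharge-status field may exist. It would solve capture, but would not tell the analyst whether to count the death.

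Finally, the study is small and descriptive, and a known death would be visible in a listing. That limits the harm but does not correct the reported proportion.

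**Conclusion.** The concern holds. The endpoint's label and its window disagree for any subject still in hospital at 72 h, and following the stated window could report 72 h survival as in-hospital survival. One such death is worth 10 percentage points at n = 10, or 20 at an assumed n = 5, always in the favourable direction.

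The mismatch of wording is certain. Actual loss of a death is only possible: it depends on length of stay, the late share of deaths and the contents of the eCRF, none of which the documents give. No test or decision rule is affected. The point should be fixed, since the numerator, denominator and proportion are the entire primary analysis.

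**What to change.** Choose one window and use it everywhere.

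**Option A, keep the label (preferred).** In Protocol 7.3, 10.8, 10.9 and Table 10.1-1 note k, and in SAP 7.4.3, state: *For the primary endpoint, vital status is recorded through discharge from the index hospitalization, even if after 72 h; a death before that discharge is a Clinical Success failure.* All other safety events keep the present window. The cost is one discharge-status field taken from the hospital record, with no extra visit or test. Records stay open for long stays, and consent wording may need a change because data would be collected after participation now ends.

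**Option B, keep the window.** Rename the component *no death through 72 h post-procedure or discharge, whichever comes first* in the Protocol synopsis, 6.2, Table 6.4-1, 11.1.1 and Table 24.2-1, and in the SAP synopsis and 3.1. This needs no new data, but the endpoint then says less about in-hospital survival.

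With either option, put the window for conversion to open heart surgery in the endpoint definition. Also align the start of the 72 h clock: the SAP synopsis follow-up row counts from enrollment, while SAP 3.2 and note k count from the procedure.

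Both options need a protocol amendment approved by the ethics committee and the Swedish Medical Products Agency (Protocol 15.3). A change to the SAP alone could settle the counting rule, but it would not correct the protocol's label or provide vital status after 72 h.
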